7.4.1 Physical Exam

The physical exam will consist of a general physical assessment of the participant.

7.4.2. Prostate Biopsy

NOTE THAT THE STANDARD- OF-CARE PROSTATE BIOPSY MUST BE PERFORMED DURING STUDY WEEK 52±1W, OR AT THE TIME THE PARTICIPANT DISCONTINUES STUDY THERAPY. If the participant discontinues study therapy to undergo a prostatectomy, tissue samples can be obtained at the time of prostatectomy.

If the participant discontinues study therapy and a prostatectomy is not planned, if at all possible, perform a biopsy prior to the participant initiating non-study therapy.

Prostate biopsies (≥ 8 core samples from all quadrants of the prostate) will be performed at end of study or at the time of study withdrawal and submitted for standard of care histopathologic grading at the participating organization.

If a study participant elects to undergo prostatectomy prior to completion of the 1-year study period (whether or not they have clinical evidence of disease progression) every effort will be made to obtain prostate tissue from the prostatectomy specimen for histology and molecular studies as described above. Data from prostatectomy samples will be viewed as exploratory.

7.4.3 Adverse Event Assessment

If, at the time of the Week 52/end of study therapy visit, the participant has not reported any adverse events, check the box at the top of the Adverse Event

Tracking Worksheet that says, "Check this box if the participant did not have any adverse events during the study"

7.4.4 Concomitant Medications

Place a check mark in the box in the "Check if Continuing at End of Study" column on the Concomitant Medications Worksheet for any concomitant medication the participant is continuing to take as of this visit.

If, at the time of the Week 52/end of study therapy visit, the participant has not reported any concomitant medications, check the box at the top of the Concomitant Medications Worksheet that says, "Check this box if the participant did not take any concomitant medications during the study".

7.4.5 Collection of Blood and Urine for Research Purposes

In addition to the blood drawn for clinical safety labs, two 3ml red top tubes and two 10ml green top tubes of blood will be collected for research assays using the supplies provided in the research lab kit. A minimum of 10ml of urine will be collected in a urine collection cup. The cup is not provided in the research lab kit. Instructions for collection, handling and shipping of research blood and urine samples are in sections 10.2 and 10.3 of this protocol.

7.5 Post-intervention Follow-up Period

There is no post-intervention follow-up period for this study.

7.6 Methods for Clinical Procedures

Not applicable.

8. CRITERIA FOR EVALUATION AND ENDPOINT DEFINITION

8.1 Primary Endpoint

The primary endpoint of the study is change in plasma IGF-1 from baseline to end of study (12 months).

8.2 Secondary Endpoints

The secondary endpoints are serum PSA doubling time (using results done for research purposes only at the CP lab at the University of Wisconsin), Gleason grade, and tumor volume on prostate biopsy, plasma and tissue biomarkers, toxicity, and compliance. Serum total PSA levels will be collected at baseline and every 3 months while on study. Gleason Grade and tumor volume will be evaluated from pre-study prostate biopsy and end of study (Wk 52) clinical pathology biopsy reports.

Plasma and tissue biomarkers will be compared from baseline to end of study (plasma) or pre-study prostate biopsy materials (within 13 months of study entry) to end of study prostate biopsy (tissue). Toxicity and compliance will be measured throughout the study as appropriate at study visits.

PSA DT will be determined from PSA values obtained during study participation (baseline and weeks 13, 26, 39 and 52). The secondary endpoint of PSA DT is based on the value at study completion (week 52 or at point of early termination). However, PSA DT will be determined starting at week 26 (the earliest time point with 3 values) and week 39 and recorded. For this initial pilot study, we will not specify the parameters for discontinuing study participation due to disease progression, as defined by PSA DT (i.e., PSA DT decreases to <2-3 years).

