Safety labs and total serum PSA (for clinical purposes, this will be processed at the PO's clinical laboratory); vital signs and weight; review of adverse events and concomitant medications; collection of blood and urine for research purposes (total serum PSA [to be analyzed at the end of study at the CP lab]; plasma and urine pharmacokinetics* and plasma biomarkers)

52 Week Visit (or End of Study Visit)

Physical exam by physician; prostate biopsy (to determine the presence or absence of tumor, the extent of tumor and Gleason scores); safety labs and total serum PSA (for clinical purposes, this will be processed at the PO's clinical laboratory); vital signs and weight; review of adverse events and concomitant medications; collection of blood and urine for research purposes (total serum

PSA [to be analyzed at the end of study at UWI], serum testosterone; plasma and urine pharmacokinetics* and plasma biomarkers), prostate tissue biomarkers (PSA, IGF-1, IGFBP-3, apoptosis (CASPASE 3), Ki-67, IGF-1R, 8OHdG and androgen receptor)

* The following PFE constituents/metabolites will be measured in plasma and urine for evidence of accumulation (trough levels): ellagic acid, dimethyl ellagic acid, dimethyl ellagic acid glucuronide (DMEAG), urolithin A, urolithin A-glucuronide, urolithin B and urolithin B-glucuronide.

NOTE: In addition to doing total serum PSA levels at the PO's clinical lab, serum will be collected to do a total serum PSA test (for research purposes only) at the University of Wisconsin's CP lab. The total serum PSA values done for research only will be used to determine end-of-study PSA doubling time (PSA-DT) results between the active and the placebo group. As a research lab, the CP lab is not CLIA-certified, and only CLIA-certified results can be used for clinical purposes.

TABLE OF CONTENTS

	Page
COVER PAGE	1
SCHEMA	3
1. OBJECTIVES	8
1.1 Primary Objectives.....	8
1.2 Secondary Objectives.....	8
2. BACKGROUND	10
2.1 Study Disease	10
2.2 Study Agent.....	11
2.3 Rationale.....	16
3. SUMMARY OF STUDY PLAN	17
4. PARTICIPANT SELECTION	18
4.1 Inclusion Criteria.....	18
4.2 Exclusion Criteria.....	19
4.3 Inclusion of Women and Minorities	20
4.4 Recruitment and Retention Plan	21
5. AGENT ADMINISTRATION	22
5.1 Dose Regimen and Dose Groups.....	22
5.2 Study Drug Administration.....	22
5.3 Run-In Procedures	22
5.4 Contraindications	22
5.5 Concomitant Medications	22
5.6 Dose Modification.....	23
5.7 Adherence/Compliance	23

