1. OBJECTIVES

1.1. Primary Objective:

The primary objective of the study is to determine the effect of Pomegranate Fruit Extract (PFE) 1000mg, taken daily for 1 year, on the plasma levels of Insulin-like Growth Factor (IGF-1) from baseline to end of study (52 weeks) in participants undergoing Active Surveillance (AS) for early stage prostate cancer.

1.2. Secondary Objectives:

- 1.2.1. To assess compliance with a once daily oral administration of PFE versus placebo over a 52-week period of time.
- 1.2.2. To assess the toxicity of PFE vs. placebo when taken daily for 52 weeks (+/- 1 week).
- 1.2.3. To compare and correlate the effect of 52 weeks of daily dosing with PFE vs placebo on the end of study biopsy results including the presence or absence of tumor, the extent of tumor and Gleason scores.
- 1.2.4. To compare and correlate biomarker modulation in response to PFE versus placebo in three areas of interest: tissue from a completely benign biopsy core, tumor tissue from a positive core, and normal tissue adjacent to tumor from a positive core. The following biomarkers will be analyzed:
 - Plasma: Insulin-like growth factor 1/IGF binding protein 3 ratio (IGF-1/IGFBP-3 ratio)
 - Prostate tissue (normal and abnormal). In order of priority:
 - apoptosis (CASPASE 3)
 - Ki-67
 - 8OHdG
 - IGF-1R
 - Androgen receptor
 - IGF-1
 - IGFBP-3
 - PSA
- 1.2.5. Measure PFE constituents/metabolites in plasma and urine for evidence of accumulation (trough levels): ellagic acid, dimethyl ellagic acid, dimethyl ellagic acid glucuronide (DMEAG), urolithin A, urolithin A-glucuronide, urolithin B and urolithin B-glucuronide.
- 1.2.6. Measure PSA doubling time (PSA DT) in serum, using the calculation provided on the Memorial Sloan Kettering Cancer Center website: nomograms.mskcc.org/prostate/psadoublingtime.aspx
- 1.2.7. To assess the feasibility of cancer chemoprevention trials in a population of men undergoing active surveillance for prostate cancer.

1.2.8. Measurement of serum testosterone.

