observed excellent tolerance and an improvement in PSA Doubling Time from 11 months pre-study to 17 months post-study as well as patients with serum PSA declines during study therapy. Carducci and colleagues (Carducci, 2009) recently completed accrual to a randomized, placebo-controlled phase I/II biomarker study of PFE (given as POMx™; 2 capsules; each capsule contains approximately 5-600 mg of polyphenols) in men undergoing prostatectomy for early stage prostate cancer. No preliminary data is available, but endpoints included tissue concentrations of ellagic acids, tissue NFkB, IGF-1/IGFBP-3, Bax/Bcl-2, CASPASE 3 and Ki67.

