13.5 Secondary Objectives

For the secondary objectives, we will compare compliance and toxicities for a once daily oral administration over a 12-month period of time between the PFE and placebo groups. We will compare the modulation of the following biomarkers with response to PFE versus placebo: plasma biomarkers, including IGF-1/IGFBP-3 ratio, total serum PSA and normal and abnormal prostate tissue biomarkers, including PSA, IGFBP-3, apoptosis (CASPASE 3), Ki-67, IGF-1R, 8OHdG and androgen receptor. We will also compare PFE constituents/metabolites for evidence of accumulation (trough levels): ellagic acid, dimethyl ellagic acid, dimethyl ellagic acid glucuronide (DMEAG), urolithin A, urolithin A glucuronide, urolithin B and urolithin B glucuronide between the treatment groups. Serum testosterone levels will also be measured.

For secondary objectives, all measurements and changes in measurements of interest will be summarized by treatment arm (and, if applicable, by visit) with appropriate descriptive statistics. Compliance, in terms of the number of pills missed, will be summarized by treatment arm with descriptive statistics, and tested for imbalance using Wilcoxon rank-sum test. Patient toxicity throughout the study will be summarized in several ways; the presence or absence of any toxicities, worst CTCAE grade, and strongest investigator-defined relationship will all be examined and characterized by treatment arm, and analyzed appropriately (Wilcoxon rank-sum for ordinal data, Fisher's exact test for dichotomous data, and log rank test for time to event data). We will examine the differences between the groups for the change from baseline for serum biomarkers, tissue biomarkers, and PFE constituents/metabolites with the appropriate tests; for dichotomous data we will use Fisher's exact test, for ordinal data we will use Wilcoxon rank-sum test, and for continuous data, and a two-sample t-test with normalizing transformation if necessary or Wilcoxon rank-sum test.

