We are also interested in the correlation of the markers and expression data with plasma IGF-1 and serum PSA doubling time. These will be tested with Pearson and Spearman correlation coefficients as appropriate; regression models will be developed to test if there is a significant relationship in the presence of treatment effect. Beyond the correlations with the primary endpoint, we are interested in exploratory analyses of the interplay various markers have with each other, and quantifying the individual contributions each make, along with baseline characteristics toward IGF-1 and PSA doubling time: we are interested in examining the complex pathways associated with the chemopreventive activities. In working toward the goal of obtaining an understanding of these relationships, we will explore the correlations and characterize the relationships among the plasma levels of the various biomarkers, the tissue biomarker measurements in normal and malignant tissue and the levels of genetic expression. Where possible, these analyses will be performed on location-matched pre- and post-treatment tumor and benign cores. When there is not a location match, we will select a post-treatment core from the nearest possible location in the prostate. In all cases, the post-treatment tumor core selected for match analysis will be of the same Gleason grade as the pre-treatment core. In addition to analyzing the expression of the selected biomarkers in pre- post-treatment matched tumor and benign cores, we will further characterize the expression of these markers across the prostate by analyzing all biopsy cores that contain cancer. Statistical techniques that may be used include, but are not limited to, Pearson and Spearman correlation analysis and multivariate regression techniques with possible transformation of the data if necessary.

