13.6 Reporting and Exclusions

As the nature of this study is exploratory, intent-to-treat should not be used as a principal analysis criterion. Nevertheless, no subjects will be excluded from the analysis and reporting, except for obvious random dropouts and for those who never took the protocol treatment.

Compliance with the protocol treatment will be measured in the form of pill counts, but the information will not be used for the primary analysis. There will be no imputation of missing data for both the primary and the secondary endpoints.

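### PSA doubling time is an analysed secondary endpoint, but the documents give no rule for a flat or falling PSA, where it is undefined or negative

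*Combined protocol and SAP*

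**What the plan says.** - Section 8.2 lists PSA-DT first among the secondary endpoints. It is computed from the research-laboratory PSA values at baseline and weeks 13, 26, 39 and 52. The value used is fixed as follows: "The secondary endpoint of PSA DT is based on the value at study completion (week 52 or at point of early termination". The same section names week 26 as the earliest time with three values and records PSA-DT from then on.
- Objective 1.2.6 gives the only method: "Measure PSA doubling time (PSA DT) in serum, using the calculation provided on the Memorial Sloan Kettering Cancer Center website". The formula and its conventions are not reproduced.
- The Schema note says that the research PSA values "will be used to determine end-of-study PSA doubling time (PSA-DT) results between the active and the placebo group".
- Section 13.5 relates the markers to plasma IGF-1 and "serum PSA doubling time. These will be tested with Pearson and Spearman correlation coefficients as appropriate", and adds regression models. Its general rule for comparing changes from baseline is, "for continuous data, and a two-sample t-test with normalizing transformation if necessary or Wilcoxon rank-sum test".
- Section 13.6 states: "There will be no imputation of missing data for both the primary and the secondary endpoints".

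No section says whether a flat or falling PSA is scored as negative, infinite, capped, a separate category, missing or excluded.

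**The concern.** Doubling time is discontinuous at zero slope. A log-PSA slope of +0.001 per year gives +693 years and a slope of -0.001 gives -693 years. Two almost identical PSA courses therefore land at opposite ends of the scale, and a slope of exactly zero has no value.

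The case is foreseeable from the protocol. Section 2.2.1 reports for an earlier trial of the extract an improvement in "PSA Doubling Time from 11 months pre-study to 17 months post-study as well as patients with serum PSA declines during study therapy". The pomegranate juice trial in Section 2.2.2 enrolled men selected for a rising PSA after local therapy, whereas criterion 4.1.1 sets only upper PSA limits. Section 8.2 describes progression "as defined by PSA DT (i.e., PSA DT decreases to <2-3 years", so longer doubling times are to be expected in men who do not progress.

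Each simple way of scoring these men has a consequence:
- With signed values, a falling PSA ranks below the fastest rise, which reverses its meaning.
- If the men are dropped, the most favourable PSA courses are lost, and more often from the active arm if the extract works. Dropping follows if an undefined value is treated as missing under Section 13.6, or if a log transformation is chosen.
- If they are ranked longest, Wilcoxon and Spearman work, but a t-test, Pearson correlation or regression on doubling time does not.

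Unless the outside calculator settles it, the choice could be made after the data are seen.

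**Working it through.** **The plan's own figure.** The only sample size stated is for IGF-1 (Section 13.2): 14 per group, two-sided 0.05. The exact two-sample t calculation at 14 per group gives power 0.800 for 1.10 SD and 0.846 for 1.17 SD; 14/0.95 = 14.7, rounded up to 15. Both reproduce. No figure is given for PSA-DT, so 14 per arm is used below.

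**Assumptions not in the documents.** Doubling time is ln 2 / b, where b is the least-squares slope of ln(PSA) on time in years. Within-man SD of ln(PSA) is 0.10 to 0.20. Between-man SD of the true slope is 0.10 per year.

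**Step 1: how often the fitted slope is not positive.** For visits at 0, 0.25, 0.5, 0.75 and 1 year, Sxx = 0.625. For one man with a given true doubling time DT, P(b ≤ 0) = Φ(-(ln 2/DT) / (SD/√0.625)). Example: DT 3 years, SD 0.10: slope 0.231, SE 0.1265, ratio 1.83, probability 0.034.

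| True DT | SD 0.10 | SD 0.15 | SD 0.20 |
|---|---|---|---|
| 3 years | 3.4% | 11.2% | 18.1% |
| 5 years | 13.7% | 23.2% | 29.2% |
| 10 years | 29.2% | 35.7% | 39.2% |

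**Step 2: imbalance from dropping, 3 versus 12 years.** With between-man variation added, the SD of a fitted slope at within-man SD 0.10 is √(0.10² + 0.10²/0.625) = 0.161. The non-positive share is Φ(-0.231/0.161) = 7.6% on placebo and Φ(-0.0578/0.161) = 36.0% on the extract, or about 1 and 5 of 14 men. At within-man SD 0.15 the shares are 14% and 39%.

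**Step 3: Wilcoxon power by scoring rule** (20,000 simulated trials, 14 per arm; within-man SD 0.10 / 0.15).

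| Doubling times | Signed | Dropped | Ranked longest | Slope |
|---|---|---|---|---|
| 3 vs 12 years | 5.5% / 6.2% | 39.7% / 20.3% | 74.0% / 48.3% | 74.4% / 49.1% |
| 2 vs 4 years | 26.1% / 8.3% | 60.5% / 31.9% | 73.6% / 49.4% | 73.6% / 49.6% |
| 3 vs 6 years | 5.7% / 4.6% | 23.5% / 13.0% | 40.4% / 25.3% | 40.5% / 25.1% |
| 15 vs 54 months (Section 2.2.2) | 75.1% / 35.3% | 100% / 96.2% | 100% / 99.5% | 100% / 99.5% |
| 11 vs 17 months (Section 2.2.1) | 97.9% / 81.7% | 98.0% / 84.8% | 98.0% / 85.5% | 98.0% / 85.5% |

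The first two rows have the same slope difference, since 1/3 - 1/12 = 1/2 - 1/4 = 0.25 doublings per year. Slope power is therefore the same up to simulation error, and the gap between those rows under signing or dropping comes from the scoring alone.

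A t-test on log doubling time with non-positive values dropped gives 38.7% / 21.0% at 3 versus 12 years, against 78.1% / 53.7% on the slope.

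**Step 4: correlations** (28 men, marker correlated 0.8 with the true slope). At a mean doubling time of 5 years, Spearman power is 6% / 6% signed, 41% / 22% dropped and 74% / 46% on the slope. Pearson gives 38% / 20% on log doubling time with dropping, against 80% / 51% on the slope. At a mean of 15 months, Spearman power is 73% at SD 0.10 and 41% to 45% at SD 0.15, whatever the scoring.

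**Step 5: range and null.** With between-man SD 0.20, 3 versus 12 years gives 6.4% / 6.4% signed, 16.4% / 12.7% dropped and 42.0% / 32.9% on the slope. With equal arms at 5 years, every test rejects in 4.1% to 5.2% of trials.

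**Step 6: short series.** Sxx for three values (to week 26) is 0.125, so the slope variance is 0.625/0.125 = 5 times that of a full series.

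**The case against.** - **The method is delegated, not absent.** Objective 1.2.6 names a calculator, which may have its own convention. This stands. A reader might infer that the plan has no method at all, but the documents support only that no rule is reproduced. A convention for displaying a doubling time would also not necessarily suit a t-test or a regression.
- **The between-arm test is inferred.** Section 13.1 and the comparison list in Section 13.5 name total serum PSA, not PSA-DT. This stands in part: the arm comparison rests on the Schema note and Section 8.2. The correlation and regression use is explicit.
- **A reader might infer that Section 13.5 forces these men out through a log transformation.** It does not. It speaks only of a normalizing transformation if necessary and offers Wilcoxon as an alternative. A reciprocal, which is in effect the slope, also fits those words for any non-zero slope.
- **A reader might infer that early stoppers are scored on any number of PSA values.** Section 8.2 ties the earliest doubling time to the first visit with three values, so a minimum is implied, though not stated.
- **The loss depends on the scenario.** This stands. At within-man SD 0.05, 2 versus 4 years gives 74% signed, 91% dropped and 94% on the slope. At 3 versus 6 years even the slope reaches only about 41% / 25%, so the endpoint is weak under any rule.
- **The trial is exploratory and this is a secondary endpoint.** True, and it limits the importance. It does not supply a value for a man whose doubling time is undefined.

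**Conclusion.** The point holds as a gap that should be closed. PSA-DT is to be analysed, and the documents do not reproduce a rule for a foreseeable group of men in whom it is undefined or negative.

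The size depends on how fast PSA rises. With slow growth, under the assumed SDs, signed scoring loses most or nearly all of the power. Dropping cuts Wilcoxon power from 74% to 40% at 3 versus 12 years, but only from 74% to 61% at 2 versus 4 years (within-man SD 0.10). A general claim that dropping halves the power is not supported: at 15 versus 54 months dropping costs at most about 3 points, although signed scoring still falls to 75% / 35%, and at 11 versus 17 months the choice hardly matters. The variances and the multi-year doubling times are assumptions; only the last two pairs come from the protocol.

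Nor does the gap inflate false positives under any one fixed rule, and it does not touch the IGF-1 primary analysis or the separate total-PSA comparison.

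**What to change.** In Sections 8.2 and 13.5, with a matching note at objective 1.2.6:

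1. Make the tested and correlated quantity each man's least-squares slope of log2(PSA) on time, in doublings per year, from the research PSA values up to week 52 or early termination. Use it for the arm comparison, correlations and regressions.
2. State the three-value minimum explicitly. List men with fewer values by arm as not evaluable for this endpoint, without imputation.
3. Tabulate PSA-DT descriptively, with stable or falling PSA as its own category.

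Minimum alternative, in one sentence: if doubling time itself is tested, non-positive slopes rank as longest and only Wilcoxon and Spearman are used. This recovers essentially all of the Wilcoxon power on the slope (74.0% / 48.3% against 74.4% / 49.1% at 3 versus 12 years).

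A mixed model of log2(PSA) on time, which gives short series less weight, is an optional sensitivity analysis and not part of the required change.

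Cost: no new visits or samples. Because Section 8.2 and objective 1.2.6 are protocol text, this needs a short amendment through the sponsor and the IRBs under Section 14.3. The slope is slightly less familiar to clinicians, which the PSA-DT table offsets, and men with fewer than three values drop out of this endpoint.

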5.6 Dose Modification

The study drug dose modification schema is as follows:

IF	THEN
The participant experiences a grade 2 adverse event that is possibly, probably, or definitely related to study drug	Stop study drug temporarily for up to 4 weeks.
The adverse event resolves to \leq grade 1 within 4 weeks:	Re-start study drug at 50% dose reduction (1 capsule should be administered every other day).
If the adverse event does not resolve to \leq grade 1 within 4 weeks:	Stop study drug permanently. Continue to follow participant per the schedule of events in Section 7.1, if participant is willing.
If the participant experiences a grade 2 event after initial dose reduction, and the adverse event is possibly, probably or definitely related to study drug:	Stop study drug permanently and follow until the adverse event is resolved to \leq grade 1. Continue to follow participant per the schedule of events in Section 7.1, if participant is willing.
In the event a subject had study drug stopped while on the 50% dose reduction, for a grade 2 adverse event that is NOT possibly, probably or definitely related to study drug	Stop study drug temporarily for up to 4 weeks. If the adverse event resolves to \leq grade 1 within 4 weeks, re-start study therapy at the 50% dose reduction level. If the adverse event does NOT resolve to \leq grade 1 within 4 weeks, permanently discontinue study drug. Continue to follow participant per the schedule of events in Section 7.1, if participant is willing.
A grade 3 or 4 adverse event occurs, regardless of relationship to study drug	Stop study drug and call protocol chair to determine if and when drug should be re-started.

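### PSA doubling times from short series count the same as those from five values over 52 weeks, and section 8.2 sets no clear minimum for the endpoint

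*Combined protocol and SAP*

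**What the plan says.** Section 1.2.6 sets the method: "Measure PSA doubling time (PSA DT) in serum, using the calculation provided on the Memorial Sloan Kettering Cancer Center website". Section 8.2 gives the data: "PSA DT will be determined from PSA values obtained during study participation (baseline and weeks 13, 26, 39 and 52"). It then gives the endpoint: "The secondary endpoint of PSA DT is based on the value at study completion (week 52 or at point of early termination"). The next sentence adds, as a qualification, "PSA DT will be determined starting at week 26 (the earliest time point with 3 values) and week 39 and recorded".

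The note in the schema says that the research PSA values "will be used to determine end-of-study PSA doubling time (PSA-DT) results between the active and the placebo group". Section 13.5 names no test for doubling time itself. Its general rule for continuous data is "a two-sample t-test with normalizing transformation if necessary or Wilcoxon rank-sum test". The same section uses doubling time in correlations and regressions with the other markers. Weighting is mentioned nowhere.

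Three provisions decide who has a short series:

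- Section 13.6 excludes obvious random dropouts and men who never took treatment, and allows no imputation.
- Section 5.6 says of several permanent stops of study drug: "Continue to follow participant per the schedule of events in Section 7.1, if participant is willing".
- Section 7.4 places the final visit at week 52 or at the end of study therapy, whichever is sooner.

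**The concern.** A doubling time is ln 2 divided by the slope of log PSA on time. The precision of that slope depends on how many values there are and how widely they are spread in time. Section 8.2 accepts whatever estimate exists when a man ends early, and section 13.5 treats all the estimates alike. With about 14 men per arm, one or two imprecise estimates can inflate the variance of the comparison by more than those men add in information. The same estimates feed the correlations with doubling time.

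The text also does not settle what happens to a man who ends before week 26. Nor does it settle which PSA values count for a man who stops agent but stays in follow-up.

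**Working it through.** **The plan's own figure.** Section 13.2 states 14 per group for the IGF-1 endpoint, two-sided 0.05. The noncentral t gives power 0.7999 at 1.10 SD and 0.846 at 1.17 SD, and 14/0.95 rounds up to 15 per group, so the figure reproduces. The plan gives no power or precision figure for doubling time.

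**Slope variance.** Var(slope) = σ²/Sxx, where Sxx is the sum of squared deviations of the sampling weeks and σ is the within-man SD of log PSA. The ratio to a completer does not depend on σ.

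| PSA values at weeks | Sxx | Variance relative to completer |
|---|---|---|
| 0, 13, 26, 39, 52 | 1690 | 1 |
| 0, 13, 26, 39 | 845 | 2 |
| 0, 13, 26 | 338 | 5 |
| 0, 13, 17 | 158 | 10.7 |
| 0, 13 | 84.5 | 20 |
| 0, 10 | 50 | 33.8 |

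The last two rows arise only if two-value estimates are allowed.

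**How many men.** The planned dropout gives 0.05 × 30 = 1.5. Section 2.1 cites 40-50% leaving surveillance over 5 years. Spread at a constant rate, which is an assumption, that is 9.7-12.9% a year, or about 3 to 4 of 30.

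**Effect on an unweighted slope comparison.** These inputs are assumptions and are not in the documents: σ = 0.15, between-man SD of true slope 0.15 per year, slope difference 0.25 per year, 14 men per arm.

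- Noise variance for a completer: (0.15 × 52)²/1690 = 0.036. Total: 0.0225 + 0.036 = 0.0585.
- Noise variance for values at 0, 13, 26: (0.15 × 52)²/338 = 0.180. Total: 0.0225 + 0.180 = 0.2025.
- One such man per arm, unweighted: the variance of the arm mean is (13 × 0.0585 + 0.2025)/14² = 0.00491. That equals 0.0585/0.00491 = 11.9 completers, fewer than the 13 left if he were omitted.
- The same man, weighted by precision: 13 + 0.0585/0.2025 = 13.3 completers.
- Two such men per arm: 10.4 unweighted and 12.6 weighted, against 12 if they were omitted.

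Simulated power (20,000 trials per case; weighted analysis with known relative weights):

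| Early stoppers per arm | t-test, unweighted | Wilcoxon | Weighted |
|---|---|---|---|
| None | 0.75 | 0.71 | 0.75 |
| One, week 26 | 0.68 | 0.66 | 0.72-0.73 |
| Two, week 26 | 0.63 | 0.62 | 0.70 |
| One, weeks 0/13/17 | 0.61 | 0.63-0.64 | 0.72 |
| Two, weeks 0/13/17 | 0.51 | 0.56-0.57 | 0.69 |

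For none, one and two week-26 stoppers per arm, the unweighted t-test gives 0.90, 0.87 and 0.83 at σ = 0.10, and about 0.58, 0.51 and 0.45 at σ = 0.20.

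**On the untransformed doubling-time scale.** I took ln 2/slope, kept negative values, and set the true doubling time in one arm at 5 years (slope 0.139 per year), with the other arm's slope 0.25 higher or lower. At σ = 0.15 the t-test has power of about 0.02-0.06. The Wilcoxon test has about 0.04-0.07 in one direction and about 0.20 in the other. These figures hardly change with early stoppers, because slopes near zero already produce huge or negative doubling times among completers.

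**The case against.** The strongest reply is that section 8.2, read as a whole, has a floor. Determination starts at week 26 with three values, so a man who ends sooner has no doubling time, and section 13.6 bars imputing one. A reader might infer from the early-termination wording that two-value estimates over a few weeks will be compared. The documents do not establish that. It is one reading of two sentences that do not fit together cleanly, because the week-26 sentence concerns when values are determined and recorded and does not say that earlier terminators lack the endpoint. Three values always span more than 13 weeks, so a span of a few weeks could only come from two values.

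Three further inferences also go too far:

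- A collapse in power. With one or two men per arm stopping at week 10, slope-scale t-test power falls to about 0.47 or 0.33. That needs two-value estimates and 2 to 4 very early stoppers among 28 men, and it applies to slopes, whereas the stated endpoint is doubling time.
- That an early stopper sits at the long end of the doubling-time distribution. Noise makes short-series slopes steep, which pulls doubling times towards zero. The huge values come mainly from completers with near-flat PSA.
- That later PSA values are discarded for every man who stops agent. Sections 8.3 and 8.4 separate off-agent from off-study, and section 5.6 keeps some of these men on schedule.

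It is also fair that no test is named for doubling time, so equal weighting is inferred from the general rule. This is one secondary measure in a 30-man exploratory study. What remains is the 5-fold variance, which arises even with the floor in place, and the absence of any weighting.

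**Conclusion.** The point holds in limited form. Even on the reading kindest to the plan, a man whose series ends at week 26 has 5 times a completer's slope variance and counts equally with him. A final visit at week 17 would make it 10.7 times. Whether two-value estimates (20 times or more) can enter is unclear and should be settled.

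The variance ratios follow from the visit schedule alone. The power figures rest on assumed PSA variability and an assumed effect: a loss of about 0.07 to 0.12 with one or two week-26 stoppers per arm, much of which weighting recovers. On the raw doubling-time scale the planned tests have very low power with or without early stoppers, which is a further reason to make the comparison on log-PSA slope. Likely few men are affected, and the IGF-1 analysis and its sample size are untouched.

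**What to change.** - In sections 8.2 and 13.5, make the between-arm PSA comparison a random-slope mixed model of log research PSA on time by arm. Use every research value up to the start of non-study prostate treatment or a 5-alpha-reductase inhibitor, including any collected after agent is stopped. Short series are then weighted by the information they carry, and a flat or falling PSA needs no special rule in the comparison.
- Report individual doubling times, and use them in the section 13.5 correlations, only for men with at least three values extending to at least the week-26 visit. State this as a condition of the endpoint.
- Reconcile sections 5.6 and 7.4 on whether a man who stops agent has his final visit then or continues on schedule, so that it is clear which PSA values will exist.

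The cost is wording and slightly more analysis work, with no new samples. The downside is that men stopping before week 26 have no individual doubling time, though their values still enter the model.
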